5.4 Quality of Life Analysis

5.4.1 Functional Assessment of Chronic Illness Therapy-Cervix (FACT-Cx) and MDASI.

QOL will be assessed using the Functional Assessment of Cancer Therapy-Cervix (FACT-Cx). The FACT-CX is comprised of 27-item general cancer concerns (FACT-G) and an additional 10-item cervical cancer specific scale. This summary score captures the FACT-G QOL dimensions of Physical, Functional, Social and Emotional Well-Being, plus the Cervical Cancer Subscale (7 items). Scoring will be done by the research personnel. The Trial Outcome Index is the sum of the Physical Well-Being (PWB), Functional Well-Being (FWB), and "additional concerns" subscales. The TOI is an efficient summary index of physical/functional outcomes. It is a common endpoint used in clinical trials, because it is responsive to change in physical/functional outcomes, sometimes more than a total (overall) multidimensional aggregated score which includes social and emotional well-being. While social and emotional well-being are very important to quality of life, they are not as likely to change as quickly or dramatically over-time or in response to therapy. The timing of the QOL and depression assessments will be administered after every two months [100, 101].

Symptom distress symptoms will be assessed by the MDASI, which assesses 13 common cancer-related symptoms, including pain, and six symptom-interference items, each rated over a 24-h recall period on a 0–10 scale. A composite interference score will be calculated as the mean of all six MDASI interference items for each patient [102, 103].

5.4.2 Demographics.

The patients' demographic characteristics will be collected before R/GI therapy and β -blockade. These include age, ethnicity, socioeconomic status, do-not-resuscitate status before and after enrollment, prior treatments, successive treatments, smoking status, baseline physical well-being (according to the TOI), and ECOG performance status.

5.4.3 The Brief Pain Inventory (BPI)

The BPI is a 9-item self-report instrument designed to assess pain in cancer and other diseases. The BPI has demonstrated reliability and validity across cultures and languages and has been used to study the effectiveness of pain treatment [104].

5.4.4 Experimental design: Translational Components

In this proposed study, we will have the benefit of obtaining blood specimens prior to and after administration of propranolol and will be able to generate preliminary data on the effects of propranolol on IL-6, IL-8, IL-10, CRP, Circulating HPV DNA and VEGF levels. These data then can be correlated with biobehavioral measures that we will collect.

5.4.4.1 IL-6:

IL-6 expression is regulated by neural and endocrine responses to stress via feedback loops and by the hypothalamic-pituitary-adrenal axis at the pituitary and adrenal gland level [105, 106]. IL-6 levels are elevated along with sympathetic activation (including cortisone and norepinephrine levels) by acute and chronic stress and depression, whereas IL-6 levels decrease following treatment of depression [83],[105] [107],[108],[109],[110],[111]. IL-6 is secreted by many cell types, including ovarian tumor cells, and is involved in many pathological processes in cancer patients. IL-6 stimulates proliferation of tumor cells [112, 113], enhances tumor-cell migration and attachment [113], promotes invasion of vascular endothelial cells by tumors [114] and angiogenesis [115], and is associated with tumor progression, shortened disease-free intervals, and poor OS [77, 116]. Oral cancer cells stressed by high levels of cortisol exhibit increased IL-6 expression and increased proliferation [111]. In melanoma cell lines, the presence of norepinephrine results in increased expression of VEGF, IL-8, and IL-6 [83]. In a study of patients with cervical dysplasia, IL-6 and IL-8 concentrations in cervicovaginal washings were higher in cervical carcinoma *in situ* (non-invasive dysplasia) patients than in normal controls and higher still in cervical cancer patients than in carcinoma

in situ patients [117]. Although relatively little data on IL-6 and cervical cancer are available, interestingly, stress hormones (norepinephrine and cortisol) can increase IL-6 mRNA production in oral squamous cell carcinoma cells, and this effect is blocked by treatment with propranolol. Researchers also have documented expression of β 1- and β 2-adrenergic receptors using polymerase chain reaction [111].

5.4.4.1.1 Methods:

IL-6 levels in plasma will be measured using enzyme-linked immunosorbent assays (ELISAs; R&D Systems, Minneapolis, MN), with results interpolated from using the standard curve provided with the ELISA kit. IL-6-expressing specimens with sensitivity below that of below the sensitivity cutoff for the regular assay will be quantitated using high-sensitivity ELISA (R&D Systems).

5.4.4.2 IL-10:

IL-10 is a counterregulatory or immunosuppressive mediator of stress-induced immunosuppression. IL-10 is extremely important to the initial transformation of cervical dysplasia to premalignant lesions. Investigators have shown that IL-10 expression is directly proportional to the development of HPV-induced cervical cancer [48]. Furthermore, in mouse models, stress-induced increases in IL-10 expression can be prevented by treatment with nadolol as well as a benzodiazepine [118]. Furthermore in a study of behavioral (telephone mediated) interventions, improvement in QOL seen in the intervention cohort was correlated with an inverse association between modulation of QOL and serum levels of IL-10 as indicated by the mean and standard error of the mean for a cohort of individual measurements [50].

5.4.4.2.1 Methods:

Serum levels of IL-10 (lower limit of detection, 0.5 pg/mL) will be measured in triplicate using standard ELISA (R&D Systems).

5.4.4.3 IL-8:

Chronic stress is associated with increase IL-8 levels [119]. IL-8 has a key role in regulation of angiogenesis, chemotaxis, and

enhancement of growth in a variety of tumors [120-122]. It is produced by tumor cells and macrophages [123]. In melanoma and ovarian cancer cell lines, treatment with norepinephrine has resulted in increased expression of VEGF, IL-8, and IL-6 [83, 119]. IL-8 contributes to the migration of tumor cells toward blood vessels and provides proliferative and antiapoptotic signals to tumor cells [124]. IL-8 overexpression is associated with advanced disease stage, high tumor grade, and decreased OS durations in cervical cancer patients [122]. IL-8 is thought to have an effect on tumor growth owing to expression of an angiogenic factor supplied by macrophages within and around cervical tumors. IL-8 expression has correlated with microvessel counts in cervical cancer patients [122], and microvessel density correlates with radioresistance and decreased OS duration [125]. Poorly oxygenated cervical tumors have increased microvessel densities, and this has correlated with decreased survival duration. Therefore, we hypothesize that IL-8 is a surrogate for angiogenesis changes that should be inhibited by the administration of propranolol.

5.4.4.3.1 Methods:

IL-8 expression in plasma will be measured using ELISA (R&D Systems), with the results interpolated from using the standard curve provided with the ELISA kit.

5.4.4.4 VEGF:

VEGF is one of the most potent proangiogenic molecules, inducing endothelial cells in vascular microvessels near tumors to proliferate and migrate and inducing alteration of their patterns of gene expression in favor of angiogenesis [126]. VEGF makes cells hyper-permeable, resulting in conditions favorable for angiogenesis in the extracellular matrix [127]. VEGF is produced by tumor cells, macrophages, and other cells. VEGF expression has been linked with norepinephrine stimulation of proliferation of cancer cell lines [83]. VEGF is critical to the growth and progression of cervical cancers and is a poor prognostic marker as consistent increases in VEGF expression are seen with increasing disease severity, and increased serum VEGF expression levels in other tumors are associated with metastatic disease and poor survival [98, 128, 129].

5.4.4.4.1 Methods:

Plasma VEGF expression will be measured using a standard ELISA kit (R&D Systems) (88). The minimum detectable serum level of VEGF = 5 pg/mL.

5.4.4.5 Circulating HPV

ctDNA can be detected in plasma of cervical cancer patients over stage I and HPV ctDNA concentration has been found to reflect tumor burden. In addition to its potential prognostic and predictive value, HPV mutation insertion is likely to constitute a new molecular surrogate of minimal residual disease and of subclinical relapse in HPV-associated tumor. This study will initially look at feasibility of obtaining this data in these patients with advanced recurrent cervical cancer [132, 133].

5.4.4.5.1 Methods

Plasma obtained from cervical cancer patients will be analyzed for HPV components in circulating cell-free DNA. DNA extraction will be performed using the Qiagen DNA extraction mini kit (Qiagen Biosciences, Germantown, MD). Quantification of target HPV genes (E2, E6, E7, L1 and L2) will be analyzed by Real-Time PCR using the Taqman Assay (Applied Biosystems, Foster City, CA). b-globin, GAPDH or b-actin will be used as a loading control. DNA concentration will be expressed as genome equivalents/per milliliter (GE/mL), as previously shown by our group (Kamat *et al.*, 2006).

5.4.4.6 Indirect calorimeter (on patients accrued at MDACC)

Cachexia is not only associated with poor outcomes, but also with an unfavorable response to drug treatment and poor quality of life. It has been observed in patients with cancer that survival is impaired already at a weight loss of 5%; Weight loss exceeding 30% is incompatible with life. It is among the most common misconceptions that one of the underlying causes of cachexia is anorexia, i.e. loss of appetite. Although anorexia is certainly a common feature of the diseases leading to the development of cachexia, this feature alone cannot explain the metabolic changes observed during this perturbation. Importantly, nutritional supplementation cannot reverse the process of losing weight in patients with genuine cachexia, which is possible in patients who suffer from starvation or anorexia. Still, nutritional aspects have to be considered when treating patients with cachexia. Weight loss in the cachectic patient predominantly affects muscle protein,

however, bone and fat tissue are likewise affected later in the course of the disease [134]. The factors that trigger the progression from clinically and body weight stable, ambulatory CHF to cardiac cachexia remain poorly understood. The timelines differ widely between patients. We will aim to see effect of Beta Blockade on resting energy use.

Using the Indirect Calorimeter (manufactured by Microlife) each patient had their oxygen consumption (V_{O_2}) and carbon dioxide production (V_{CO_2}) measured until recordings were in a steady state for 15–20 min. The total energy expenditure was calculated to determine the measured resting energy expenditure (MREE) under conditions of rest. The oxygen and carbon dioxide sensors were calibrated for accuracy before each measurement. Use of the indirect calorimeter takes roughly 15 minutes. Resting Energy Expenditure: Formulae for measuring resting energy expenditure (REE), such as the Harris-Benedict equation, may underestimate an individual's caloric requirements [135, 136]. A more accurate measurement of the REE can be made using indirect calorimeter. Each individual's REE measurement will take approximately 10-15 minutes using a handheld indirect calorimeter (MedGem 101, (MG); HealthTech, Golden, CO), at baseline (+/- 3 days) and at day 58 (+/- 3days). Measurements with the MG indirect calorimeter used single-use disposable mouthpieces and a noseclip for collection of expired air. Using the MG indirect calorimeter each patient has their oxygen consumption (V_{O_2} (ml/min)) measured and REE (kcal/day). [2]

6.0 SAFETY PLAN AND CRITERIA FOR REMOVAL FROM STUDY

6.1 Patient Safety

A number of measures will be taken to ensure the safety of patients participating in this trial. These measures will be addressed through exclusion criteria (see Section 3.2) and routine monitoring as follows:

Patients enrolled in this study will be evaluated clinically and with standard laboratory tests before and at regular intervals during their participation in this study. Safety evaluations will consist of medical interviews, recording of adverse events, physical examinations, blood pressure, and laboratory measurements (see Section 8.1). Patients will be evaluated for adverse events (all grades), serious adverse events, and adverse events requiring study drug interruption or discontinuation at each study visit for the duration of their participation in the study. Patients discontinued from the treatment phase of the study for any reason will be evaluated approximately 30 days (28-42 days) after the decision to discontinue treatment.

6.2 Criteria for Removal from Study

- 6.2.1 Patients will be removed from the study if they are unable to tolerate the lowest doses of the regimen because of toxicity.
- 6.2.2 Patients may withdraw from the study at any time for any reason.

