7.0 TREATMENT MODIFICATIONS

Propranolol can be dose reduced if the patient's heart rate is less than 60 or systolic BP is less than 110 or diastolic less than 50 and showing symptoms at two different timepoints 24 hours apart. Also if the patient has side effects from the beta-blocker a dose reduction can be performed as outlined in Table E. All dose reductions will be made in the clinic. The maximum dose for propranolol should be 40mg po twice a day. For patients > 65 years old the maximum dose will be 20 mg by mouth twice a day. All dose adjustments will be made in the clinic.

Table E Modifications for Propranolol dosing

	Regimen -1 Level	Regimen -2 Level
Starting Dose 20 mg twice daily	10 mg po bid (50%)	Discontinue
Maximum Dose 40 mg twice daily	30 mg po bid (25%)	20 mg po bid (50%)

7.1 Hypotension.

Patients receiving propranolol should be monitored before each dose with measurement of blood pressure (see Section 5.0 Treatment Plan). If the SBP is less than 110 or the DBP is less than 50 and showing symptoms at two different timepoints 24 hours apart, the patient should be dose modified to regimen level -1 (see Table E). If after this dose modification there is still hypotension, then dose modify to regimen level -2 (see Table E). If patient still encounters hypotension, then discontinue the propranolol.

7.2 Bradycardia.

Patients receiving propranolol should be monitored with a measurement of heart rate. If the heart rate is less than 50 or 50-60 and showing symptoms at two different timepoints 24 hours apart, the patient should be dose modified to regimen level -1 (see Table E). If after this dose modification there is still bradycardia, then dose modify to regimen level -2 (see Table E). If patient still encounters bradycardia, discontinue propranolol.

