8.0 STUDY PARAMETERS AND SERIAL OBSERVATIONS

8.1 Observations and Tests

The following observations and tests are to be performed and recorded.

Observations and Tests	Prior to Initial Study Treatment	On Treatment			
		Month 1 (+/- 7 days)	Month 2 (+/- 7 days)	Month 4 (+/- 7 days)	End of Study (+/- 7 days)
History & Physical	1			4	
Blood Pressure	1	8	8	8	8
Heart Rate	1	8	8	8	8
Toxicity Assessment	1	8	4	4	4
CBC/Differential/Platelets	1		4	4	4
Serum Creatinine	1		4	4	4
Bilirubin, SGOT, SGPT, Alkaline Phosphatase	1		4	4	4
Magnesium	1		4	4	4
C-Reactive Protein (CRP)	1		4	4	4
PT/INR, PTT	1		5	5	
Serum Pregnancy test if childbearing potential exists	1				
EKG	1		6	6	
Indirect Calorimetry (MDA Pts. Only)	1		4	4	
Palliative Supportive Care	1		6	6	
QOL Surveys	3		7	7	
Demographic information	3				
Blood draw (TR)	3		7	7	
MRI, PET or PET/CT Scan of Chest/Abd/Pelvis	2		6		
Pill Diary		8	4	4	4
Relaxation Log		8	4	4	4

1. Must be obtained within 14 days prior to initiating propranolol therapy.
2. Must obtain CT, MRI or PET within 6 weeks prior to receiving any propranolol therapy.
3. QOL Surveys (MDASI, HADS, BPI, and FACT-Cx), demographic information and translational blood to be performed prior to initial study treatment
4. Must be obtained within +/- 7 days prior to clinic visit.
5. For patients on prophylactic or therapeutic anticoagulation with warfarin, PT/INR should be monitored before.
6. Only if clinically warranted.
7. Biobehavioral measures and QOL Surveys (MDASI, HADS, BPI, and FACT-Cx) are to be administered after completion of months 2 & 4 on trial and blood is to be drawn at clinic visit for translational purposes.

8. Blood Pressure and Heart Rate will be checked prior to starting propranolol in the clinic by research nurse/clinic nurse. At 48-72 hours after starting treatment, blood pressure monitoring needs to be done in the clinic by research nurse/clinic nurse but if patient unable to return to clinic, research personnel will contact patient for blood pressure readings. After that time, patient should continue to monitor blood pressure daily with their personal blood pressure machine, at their local pharmacy, or in the clinic. If personally monitoring their blood pressure, the patient should contact the research nurse if the SBP is less than 110, the DBP is less than 50 or heart rate 50-60 and showing symptoms at two different timepoints 24 hours apart.

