3. $\Pr(\pi_t \leq 0.2 \mid \text{data}) > 90\%$ where π_t is the proportion of any grade 3-4 toxicities that are probably, possibly, or definitely related to the intervention.

Scores for the FACT-Cx can be calculated when at least 50% of the items on each subscale have been answered. A total score for the FACT-Cx can be calculated when at least 80% of the total items have been answered and each subscale has a score.

Scores for BPI: Pain Severity can only be calculated when all 4 items have been answered. Scores for BPI: Pain Interference can be calculated when at least 4 out of the 7 items have been completed.

Scores for HADS: Anxiety can be calculated when at least 6 of the 7 anxiety items have been completed. Likewise, scores for HADS: Depression can be calculated when at least 6 of the 7 depression items have been answered.

Scores for MDASI: Symptom Severity can be calculated when at least 7 of the 13 items have been completed. Scores for MDASI: Symptom Interference can be calculated when at least 4 of the 6 items have been completed.

Patients are considered nonevaluable if they leave the study through disease-specific death or progressive disease prior to Month 4, and they will not be replaced. Disease-specific death does not include death due to excessive toxicity. All other patients are considered evaluable. In addition to calculating the percent of women who complete these quality of

life (QoL) measures, we will calculate the percent of women completing combined intervention of twice daily beta blocker and twice weekly progressive muscle relaxation and guided imagery at Month 2 and Month 4.

The secondary objectives of this study are to estimate the impact of beta blocker and relaxation intervention on symptoms, anxiety, depression, pain and QoL. We will examine symptoms and symptom distress using the MDASI, anxiety and depression using HADS, pain using the BPI and QoL using the Trial Outcome Index (TOI) of the FACT-Cx.

The exploratory objectives of this study are to measure changes in serum levels of IL-6, IL-8, IL-10, VEGF, CRP, and resting energy use via calorimeter, as well as to measure HPV components (e.g. E6 and E7) in circulating cell-free DNA.

All secondary and exploratory endpoints will be examined graphically and through summary statistics. Ninety percent confidence intervals will be calculated for all endpoints, including feasibility endpoints.

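### Removal from study for intolerance ends the Month 2 and Month 4 surveys while the patient stays in the denominator, so the survey criterion mixes drug intolerance with survey completion

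*Combined protocol and SAP*

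**What the plan says.** Three passages describe what happens when a patient cannot tolerate the drug, and they differ:

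- Section 6.2.1: "Patients will be removed from the study if they are unable to tolerate the lowest doses of the regimen because of toxicity".
- Section 7.2, after the dose steps are exhausted: "If patient still encounters bradycardia, discontinue propranolol". Section 7.1 does the same for hypotension. Neither mentions leaving the study.
- Section 6.1: "Patients discontinued from the treatment phase of the study for any reason will be evaluated approximately 30 days (28-42 days") after the decision to stop. This implies a treatment phase distinct from the study as a whole. No survey is named for that evaluation.

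On survey timing, footnote 7 to the table in section 8.1 says the instruments "are to be administered after completion of months 2 & 4 on trial". The rows for QOL surveys and translational blood have entries at baseline, Month 2 and Month 4, and none under End of Study.

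On the denominator, section 12.0 says: "Patients are considered nonevaluable if they leave the study through disease-specific death or progressive disease prior to Month 4". It adds "Disease-specific death does not include death due to excessive toxicity" and then "All other patients are considered evaluable". Section 9.0 defines evaluability the same way. A patient removed for intolerance is therefore evaluable.

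The survey criterion (sections 9.0 and 12.0) requires calculable FACT-Cx, BPI, HADS and MDASI scores for all evaluable patients at baseline, 13 of 15 at Month 2 and 11 of 15 at Month 4. Toxicity is a separate criterion in section 12.0: a posterior probability above 90% that the proportion with related grade 3-4 toxicity is at most 0.2.

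**The concern.** If removal from the study is taken literally, a living patient who has stopped propranolol is no longer offered the remaining surveys but is still counted in the survey proportion. The plan does not say outright that she is scored as a miss. It follows from the definition of evaluable, because no score can be calculated for a survey that was not given.

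Two things are at stake. First, a shortfall on the survey criterion could mean that these women cannot or will not complete four instruments, or that some of them could not take the drug. Objective 1.1.1 asks the first question, and the reported percentage would not separate the two. Second, secondary objective 1.2.2 concerns change in symptoms, mood, pain and quality of life. The values lost would be those of the patients who tolerated propranolol worst, and section 12.0 describes no handling of such missing data.

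**Working it through.** **The plan's own figures.** Exact (Clopper-Pearson) 90% intervals: 13/15 gives 63.7% to 97.6%, and 11/15 gives 48.9% to 90.3%. Section 12.0 states 64% to 98% and 49% to 90%, so its figures reproduce.

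**Inputs.** Evaluable patients n = 15, thresholds 13 and 11 (section 12.0). The removal rate q is not in the documents; I assume 5% to 20%, cumulative to the time point in question. I also hold n at 15, although section 9.0 says nonevaluable patients will be replaced and section 12.0 says they will not.

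**Slack in the rule.** Month 2 allows 15 − 13 = 2 misses; Month 4 allows 15 − 11 = 4. With every other survey scorable:

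- 2 removals before Month 2: 13/15 = 86.7%, met with no slack left.
- 3 removals before Month 2: 12/15 = 80%, not met.
- 4 removals before Month 4: 11/15 = 73.3%, met with no slack left.
- 5 removals before Month 4: 10/15 = 66.7%, not met.

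**Chance of meeting the criterion.** With X removals distributed Binomial(15, q):

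P(Month 2 met) = P(X ≤ 2) = Σ(k = 0 to 2) C(15,k) q^k (1−q)^(15−k)

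At q = 0.10 this is 0.206 + 0.343 + 0.267 = 0.816. For Month 4 the sum runs to k = 4.

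| Assumed q | Month 2 met | Month 4 met |
|---|---|---|
| 5% | 0.964 | 0.999 |
| 10% | 0.816 | 0.987 |
| 15% | 0.604 | 0.938 |
| 20% | 0.398 | 0.836 |

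**Effect of still seeking the surveys.** Assume 95% scorable surveys among patients not removed, and a fraction s among those removed. The per-patient probability is 0.95(1−q) + s·q.

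| q | s | Per patient | Month 2 met | Month 4 met |
|---|---|---|---|---|
| 10% | 0 | 0.855 | 0.626 | 0.945 |
| 10% | 70% | 0.925 | 0.903 | 0.996 |
| 20% | 0 | 0.760 | 0.264 | 0.719 |
| 20% | 70% | 0.900 | 0.816 | 0.987 |

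**Overlap with the toxicity criterion.** The prior is not stated. Suppose 3 related grade 3-4 events. With assumed priors Beta(1,1), Beta(0.5,0.5) and Beta(0.2,0.8), the posterior probability that the proportion is at most 0.2 is 0.40, 0.47 and 0.55 with 15 patients, and 0.63, 0.70 and 0.76 with 20. All are below 0.90. Three removals for such events would fail the toxicity criterion anyway. Section 7's triggers are blood pressure and heart rate readings and side effects, not toxicity grades, so removals below grade 3 are possible. Those count only against the survey criterion.

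**The case against.** The strongest reply is that the denominator is deliberate. Both sections that define evaluability keep toxic deaths in, and such patients cannot complete later surveys. Sections 5.3 and 10.0 also tie feasibility to completing the three time points, not to completion among those offered a survey. This stands: toxicity losses belong in the denominator. It does not explain why a living patient off propranolol should not be asked for her surveys.

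The size is also open to challenge. Section 2.11 presents propranolol as having few side effects, and dose reduction is allowed before removal. At a 5% removal rate the Month 2 target is still met 96% of the time. The secondary analysis is descriptive, with 90% intervals and no test. These points limit the consequence but do not remove the mechanism.

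A reader might infer more than the documents support:

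- *Every toxicity removal is a survey failure.* Not so. Removal after the Month 2 survey affects Month 4 only, and removal after Month 4, when patients may continue by choice, costs nothing.
- *Removed patients yield no further outcome data.* Not so. The End of Study column includes toxicity, laboratory tests, CRP (a named exploratory endpoint) and both diaries, and patients are followed to death through medical notes. What is lost is surveys, translational blood and calorimetry.
- *The two primary objectives collapse into one.* Not so. Section 12.0 calculates completion of the combined intervention as its own percentage.
- *The protocol firmly equates stopping drug with leaving.* Section 6.2.1 does, but sections 6.1 and 7 point the other way. The text is inconsistent on this.

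**Conclusion.** The point holds in a limited form. Sections 6.1, 6.2.1 and 7 must be reconciled. Under the literal reading of 6.2.1, a removal before Month 2 costs two survey time points and one between Months 2 and 4 costs one, with the patient still counted. Three or five such removals respectively are enough to fail the criterion even if every survey offered is completed. The pass probabilities rest on assumed removal rates, independent patients and a fixed 15.

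The overall feasibility verdict is most exposed when removals are below grade 3; related grade 3-4 events already weigh on the toxicity criterion. Apart from the verdict, the loss of survey data is selective, which is reason enough to act. I class this as a cheap improvement, not as an error that invalidates the design.

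**What to change.** In section 6.2.1 and footnote 7 of the section 8.1 table, state that stopping propranolol does not end survey collection. The Month 2 and Month 4 surveys are still sought at their scheduled times unless the patient withdraws consent, and the existing 24-hour HADS scoring and physician review apply to them. Align sections 6.1 and 7 with this wording.

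Keep these patients in the denominator. Report survey completion with and without surveys obtained off propranolol, and list missed surveys by reason (intolerance, refusal, too ill, other).

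Adding a survey or translational blood draw at End of Study would not do the same job. A survey on an arbitrary date is neither a Month 2 nor a Month 4 score, and objective 1.3.1 concerns markers during propranolol treatment, which a sample taken after weaning would not address.

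The cost is a few sentences of protocol text, some follow-up contact, and a small number of off-drug surveys that must be identified in the analysis. If surveys are collected outside the clinic, the 24-hour HADS step needs a workable route. No dose or stopping rule is affected.
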